#### **8.4 Unanticipated Problems**

An Unanticipated Problem is any event, incident, experience, or outcome that is

- unexpected in terms of nature, severity, or frequency in relation to
  - the research risks that are described in the IRB-approved research protocol and informed consent document; Investigator's Brochure or other study documents;
  - the characteristics of the subject population being studied (persons with life threatening COVID-19); and
- possibly, probably, or definitely related to participation in the research; and
- places subjects or others at a greater risk of harm (including physical, psychological, economic, or social harm) than was previously known or recognized.

Unanticipated Problems will be reported in WebDCU. Unanticipated problems may include problems with protocol implementation, participant safety, and/or concerns regarding informed consent. Initial reports will be submitted within 7 calendar days of site awareness of the event.

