# 1. Protocol Summary

## 1.1 Brief Synopsis

Title	Clinical-trial of COVID-19 Convalescent Plasma in Outpatients (C3PO)
Protocol Number	Pro00044489
Phase	Phase III
Methodology	Multi-center, randomized, single-blind, two-arm, placebo-controlled trial with blinded outcome assessment.
Study Duration	June 2020 to July 2021
Study Center(s)	SIREN Trial Network
Objectives	
Primary: To determine the efficacy and safety of a single dose of convalescent plasma (CP) for preventing the progression from mild to severe COVID-19 illness.
 
Secondary: Characterize the immunologic response to CP administration.

Endpoints	
Primary:
 
Disease progression defined as death or hospital admission or seeking emergency or urgent care within 15 days of randomization.
 
Secondary:
 
 
• Worst severity rating on the WHO's COVID Ordinal Scale for Clinical Improvement during the 30 days following randomization
 
• Time to disease progression on the COVID Outpatient Ordinal Outcome Scale censored at 15 days after randomization.
 
• Hospital-free days during the 30 days following randomization
 
• All-cause mortality at 30 days
 

	
 
• Symptom inventory measured using the CDC list of COVID-19 symptoms on days 2, 4, 6, 8, 10, 14, 15, 30
 
• Neutralizing antibody titers at days 0 (pre-intervention and post-intervention), 15, and 30
 
• Spike protein IgG antibody titers pre and post CP administration
 

Number of Subjects	Original planned maximum sample size: 600 (300 per arm) Revised maximum sample size based on planned re-estimation: 900 (450 per arm)
IND Sponsor	[name], MBA
Main Inclusion Criteria	
 
• One or more symptoms of COVID-19 illness and laboratory-confirmed SARS-CoV-2 infection.
 
• Has at least one study defined risk factor for severe COVID-19 illness
 
• Clinical team deems stable for outpatient management without new supplemental oxygen
 
• CP available at the site at the time of enrollment
 
• Duration of symptoms <math>\leq</math> 7 days at ED presentation and randomization
 
• Informed consent from subject
 

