## Study Population

Adults presenting to the emergency department (ED) with their first episode of symptomatic, laboratory-confirmed COVID-19 illness, who are at high risk for progression to severe/critical illness, but who are clinically stable for outpatient management at randomization.

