Has at least one study defined risk factor for severe COVID-19 illness:	Age is biological age. Hypertension must be treated with medications. Diabetes must be treated with medications. Chronic lung disease, coronary artery disease, chronic kidney disease  per medical record. Immunosuppression with	Age, hypertension, diabetes, coronary heart disease, chronic lung disease and chronic kidney disease are associated with higher COVID-19 morbidity and mortality.  Hypertension and diabetes are on a continuum and sometimes controlled without

	
medications.
 
Obesity is defined as <math>BMI \geq 30</math>
 
Sickle cell disease is based on past medical history
	
medications. We will restrict to medication-treated conditions in order to clearly define comorbidities that have prompted medical treatment. Patients on immunosuppression for solid organ transplants are more often hospitalized for severe COVID-19 illness. Emerging data suggests that sickle cell disease and obesity are risk factors for severe disease.

ED team deems stable for outpatient management without new supplemental oxygen requirement	
Plan is to not place patient in inpatient bed, but to discharge from emergency department without supplemental oxygen (patients intended for observation for <24 hours or <2 midnights in an outpatient observation unit without oxygen supplementation would be eligible). Patients discharged from the ED may be brought back for randomization and treatment so long as they meet study inclusion criteria at the time of randomization.
	
Illness is mild, which allows potential to observe progression. Supplemental oxygen use would imply that the patient has little physiological reserve and already is at the verge of primary outcome.

ABO-compatible CP available at the site at the time of enrollment	Blood bank to check blood type	Must be able to deliver intervention.
Duration of symptoms $\leq 7$ days at ED presentation and randomization	Subject report of symptom onset	CP therapy is most likely to have benefits early in the course of illness.
Signed informed consent	Informed consent document	Subject understands the risk and details of the trial

Immunocompromised: Any condition that causes reduced ability to fight infections. This may be caused by certain diseases (eg: cancer, diabetes); genetic disorders (eg: severe combined immune deficiency); or medications (eg: steroids, chemotherapy)

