#### Algorithm to Determine Relatedness of Adverse Event to Study Agent

Not Related	The temporal relationship between treatment exposure and the adverse event is unreasonable or incompatible and/or adverse event is clearly due to extraneous causes (e.g., underlying disease, environment)
Unlikely	Must have both of the following 2 conditions, but may have reasonable or only tenuous temporal relationship to intervention. 
 
• Could readily have been produced by the subject's clinical state, or environmental or other interventions.
 
• Does not follow a known pattern of response to intervention.
 

Reasonable Possibility	Must have at least 2 of the following 3 conditions 
 
• Has a reasonable temporal relationship to intervention.
 
• Could not readily have been produced by the subject's clinical state or environmental or other interventions.
 
• Follows a known pattern of response to intervention.
 

Definitely	Must have all 3 of the following conditions 
 
• Has a reasonable temporal relationship to intervention.
 
• Could not possibly have been produced by the subject's clinical state or have been due to environmental or other interventions.
 
• Follows a known pattern of response to intervention.
 

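### The Unanticipated Problem definition uses life-threatening COVID-19 as its reference population, but the trial enrolls mildly ill, stable outpatients

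*Combined protocol and SAP*

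**What the plan says.** Section 8.4 sets three joint conditions for an Unanticipated Problem. The first is that the event is "unexpected in terms of nature, severity, or frequency in relation to" two comparators. One is the set of research risks described in the study documents. The other reads "the characteristics of the subject population being studied (persons with life threatening COVID-19); and". The second condition is that the event is "possibly, probably, or definitely related to participation in the research; and". The third is that it exposes subjects or others to more risk of harm than was previously recognized. Sites enter such problems in the trial database, and the initial report is due within 7 calendar days of the site becoming aware.

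The enrolled population is described elsewhere:

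- The Study Population paragraph of Section 1.2 specifies adults "who are at high risk for progression to severe/critical illness, but who are clinically stable for outpatient management at randomization".
- The main inclusion criteria in Section 1.1 include "Clinical team deems stable for outpatient management without new supplemental oxygen".
- The rationale column in Section 5.1 explains this criterion with the words "Illness is mild, which allows potential to observe progression".
- The protocol's title page also refers to mild illness.

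**The concern.** The parenthesis is part of the test. It tells a site which patients to have in mind when it asks whether an event was unusual in kind, severity or frequency. In people whose COVID-19 is already life-threatening, intubation, shock or death would surprise nobody. In people well enough to go home, the same event soon after an infusion deserves a second look.

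The direction of the error matters because of a risk the protocol itself names. Section 2.3.1 discusses antibody-dependent enhancement and undertakes to watch illness severity for signs of it. Enhancement would appear as unusually severe COVID-19 in people who entered with mild disease. A life-threatening benchmark is least sensitive to exactly that pattern. What is at stake is whether such an event also gets the 7-day Unanticipated Problem report.

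**Working it through.** The documents state no figure on this point, and none is needed. The check compares wording and then traces what else would capture the event.

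**1. Do the descriptions conflict?** Section 8.4 says life-threatening disease. Sections 1.1, 1.2 and 5.1 say mild disease, stable, no new oxygen. Being at high risk of progression, as Section 1.2 puts it, is not the same as having life-threatening illness at entry. The conflict is direct. It is in current text rather than the amendment history, and nothing elsewhere in the protocol explains the 8.4 wording.

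**2. What does the conflict change?** Take a participant who is intubated shortly after infusion.

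- Against the population named in 8.4, the severity is ordinary. The first condition can fail, and with it the classification, because all three conditions must hold.
- Against the enrolled population, the severity is notable and this comparator can be met. The event must still be related to participation and imply greater risk.

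So the parenthesis can block a classification, but correcting it does not by itself create one.

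**3. What captures the event regardless?**

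- Section 8.3.2 counts death and life-threatening events as serious.
- Section 8.3.5 requires serious events to be entered within 24 hours of discovery, with no expectedness condition. The independent medical safety monitor is notified automatically, reviews within 2 business days, and records an assessment of relatedness and expectedness.
- Section 8.2.1 continues serious-event reporting to the end of study and adds a Day 30 record review. It also asks for any event leading to admission or an emergency or urgent care visit, even if non-serious.
- Section 10.2 has the monitor decide whether a serious event is possibly related and unexpected, which triggers expedited reporting to the FDA and the central IRB. It also has the DSMB review safety reports.

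None of these provisions refers to the parenthesis in 8.4.

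**4. Where are those routes less than complete?**

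- After ED discharge, Section 8.3.5 limits reporting to serious events, which is narrower than Section 8.2.1. The two should be reconciled.
- Section 8.3.2 separately lists respiratory failure and shock among events to be anticipated in admitted COVID-19 patients. An expected label can therefore arise without 8.4.

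Neither point removes capture of a death or life-threatening event as a serious adverse event.

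**The case against.** The strongest reply is that this is a slip of wording with little practical effect. Serious events reach the database and the monitor whatever 8.4 says, the monitor rather than the site decides expectedness for expedited reporting, and expectedness is one of three conditions in 8.4. Most of this stands and sets the limits of the point. It does not remove the defect: 8.4 is operative text, it carries its own 7-day clock, and it names the wrong patients.

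Three stronger readings are tempting, and the documents do not support them.

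**That severe deterioration would go unreported, or be screened out at the site.** Section 8.3.5 requires entry of serious events with no expectedness condition. The supported statement is that the event may not be reported as an Unanticipated Problem.

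**That the error can be sized.** Sections 1.2 and 2.2 give about 5% of cases becoming critical and as many as 50% of those dying. A reader might set 50% against 0.05 × 0.50 = 2.5% and infer a 20-fold error. But 0.50 / 0.025 = 1 / 0.05 = 20, so the fatality figure cancels and the ratio only restates the 5% share. Neither group is the enrolled one, the sum assigns every death to critical cases, and no rule in 8.4 uses a background rate.

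**That the relatedness wording in 8.4 should be replaced by the grades in Section 8.3.4.** The vocabularies do differ, but so do the questions. Section 8.3.4 grades an adverse event against the study agent. Section 8.4 asks about participation in the research and also covers consent and implementation problems, which those grades cannot handle. The swap could also do harm. An unexplained COVID-like deterioration after infusion has a reasonable temporal relationship, could readily come from the disease, and follows no known reaction pattern. That meets one condition, whereas the Reasonable Possibility grade says "Must have at least 2 of the following 3 conditions". The event meets both conditions for Unlikely, so it would be excluded, while the present wording can include it.

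**Conclusion.** The concern holds in a limited form. Section 8.4 measures expectedness against a population the trial does not enroll, and the error runs toward treating severe deterioration as expected. The consequence is a less sensitive Unanticipated Problem test and a possible missed 7-day report through that route. Capture as a serious adverse event and review by the independent monitor are unaffected, as are the sample size, the analysis and the error rates.

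This rests on two assumptions: that sites apply the parenthesis literally, and that the monitor does not use it when assessing expectedness. The documents do not tie the monitor's assessment to it, but they name no other reference population for that assessment. The error is an internal inconsistency worth correcting. It is not evidence that harm would pass unseen.

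**What to change.** In Section 8.4, replace the parenthesis with a description of the people enrolled, for example: *(adults with mild COVID-19 at risk of progression, assessed as stable for outpatient management)*. Leave the relatedness condition in 8.4 unchanged.

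The edit is one phrase. Section 10.1.1 sends protocol modifications to the central IRB, so it needs that approval, and sites should be told. It may produce a few more Unanticipated Problem reports. It will not alter the list of anticipated events in Section 8.3.2, which remains a separate route to an expected label.

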## **9. Statistical Considerations**

This trial is designed with sample size re-estimation to adapt to the evolving landscape of COVID-19 illness. This trial design, as well as its implementation mechanics, can serve as a template for subsequent studies of how interventions delivered to patients presenting to the emergency department alter disease trajectory.

We believe that clinicians will change practice if CP can afford ~10% absolute risk reduction in disease progression, but the constrained sample size limits power to detect clinically significant changes if the control event rate for hospitalization, the most important sign of worsening, is too low.

For this reason, we will look at a composite outcome that combines hospitalization, symptom progression that results in seeking medical evaluation or treatment (ED visit or urgent clinic visit), and death outside of the hospital. The total event rate for this composite will be larger than hospitalization alone.

In addition, we have selected a population with risk factors for more severe disease, based on the case series reported to date: older age and chronic end-organ disease or comorbidities. The event rate for the primary outcome is expected to be higher in this population than in all outpatients with COVID-19. Further, this population is the one with most potential to benefit from CP therapy and is the most likely outpatient population in whom clinicians may choose to use a blood product.

We considered comparing time to event as an alternative to comparing proportions of events between the treatment arms. The gain in power from time to event analysis is offset by the concern that the time to event is affected more by the time course of the illness than by initiation of treatment, and that patient self-report of the day of symptom onset will not be sufficiently accurate to adjust. For example, a patient who presents to the ED and is enrolled on day 7 of

COVID-19 illness may progress to hospitalization more quickly than a patient who presents to the ED and is enrolled on day 2 of COVID-19 illness. In our chosen analysis, the similar worsening of illness in both patients is accurately captured by counting the presence of the primary endpoint by Day 15. Moreover, a delay in disease progression is not clinically important if the proportion of subjects who progress is not different.

### 9.1 Sample Size

Sample size is restricted by the availability of CP for the participating sites. Based on discussions with the NHLBI, we are assured to have sufficient CP available for roughly 300 patients at the time of study initiation.

Therefore, we provide power estimations based on our primary outcome, assuming a maximum of 600 randomizations (300 per group).

Figure 1 provides a range of risk differences (control minus treatment) based on potential event rates for our control population. For example, if the primary outcome event proportion within 15 days from randomization is 20% in the control population, then we have 85% power to detect an absolute decrease of at least 10% in this proportion for those treated with CP. If the control proportion is less than 20% then we can detect differences of roughly 8% while maintaining more than 80% power. Alternatively, if the control rate is closer to 30%, then our power begins to drop for detecting risk differences less than 10%. Based on the current information on hospitalizations in this COVID population, we do not expect the proportion in the standard of care arm to vary greatly from 20%. Clinicians are unlikely to discharge patients whose risk for the primary outcome is significantly greater than 30%..

[figure not shown]
#### Sample Size Re-Estimation

We recognize that sample size estimation is based on assumptions and, if our control proportion greatly varies from what we assumed, then we may begin to see a decrease in power. To reduce the likelihood of an underpowered study due to an incorrect assumption, we propose to conduct a sample size re-estimation at the time of the first interim analysis. The overall primary outcome proportion of the population will be estimated using the interim data for the sole purpose of sample size re-estimation (not for interim testing of a treatment effect). If the observed overall event rate is greater than the assumed, then we may require additional subjects to maintain adequate power. Ultimately it is the DSMB's decision to recommend an increase in the total sample size and this decision should take into account the safety profile, which will be provided to the DSMB at the time of analysis. Based upon the DSMB's recommendation, the study team in conjunction with NHLBI will need to determine the feasibility of an increase to the sample size in terms of the availability of additional units of CP and impact on funding. We do not plan to decrease the sample size based on the re-estimation plan.

### 9.2 Analysis Plan

#### 9.2.1 Primary Analysis

Outcomes will be analyzed using the intent-to-treat principle (ITT). The primary analysis for this trial is to test the hypothesis of superiority of CP as compared to saline in the ITT population. To

test this hypothesis, the posterior probability that the proportion of primary outcome events at 15-days post randomization is higher in the saline arm as compared to the CP arm will be calculated. Because little is known about the impact of CP, we assume a non-informative beta distribution for the prior probability. The primary null hypothesis (that the CP proportion is greater than or equal to saline) will be rejected if the posterior probability is greater than or equal to 0.975 (selected to coincide with a one-sided alpha level of 0.025 under a frequentist design). The treatment effect and corresponding credible interval will be constructed.

If the trial fails to enroll the planned sample size due to a significant decrease in the number of COVID-19 patients, then Bayesian posterior and predictive probabilities will be used to assist in the interpretation of the observed data.

Secondary analyses of the primary outcome will explore the impact of potential prognostic variables including age, sex, onset of symptoms duration and site. A logistic regression model will be used for these additional analyses. We will also examine whether participants' pre-treatment antibody levels and/or the genotype of the SARS-CoV2 virus that they carry modify the association between CP and outcome.

The inherent variability in antibody titer among CP units will provide an important opportunity to explore the dose-effect relationship for CP. We envision performing a similar regression of the primary outcome using CP titer categories.

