### Randomization

A web-based central randomization system will assign treatment using a fixed 1:1 allocation ratio. The randomization algorithm will prevent possible selection bias by providing random treatment assignment to each subject and prevent accidental treatment imbalances in age and site.

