## 5. Study Population

### **5.1 Inclusion Criteria**

- One or more symptoms of COVID-19 illness
- Laboratory-confirmed SARS-CoV-2 infection
- Has at least one study defined risk factor for severe COVID-19 illness:
  - Study defined risk factors initially include: age $\geq$ 50 years; hypertension; diabetes; coronary artery disease; chronic lung disease; chronic kidney disease; immunosuppression; sickle cell disease, and obesity (body mass index [BMI] $\geq$ 30) and are updated as needed in the C3PO Manual of Procedures in response to changes in CDC guidance or other information.
- Clinical team deems stable for outpatient management without **new** supplemental oxygen

- ABO-compatible CP available at the site at the time of enrollment
- Duration of symptoms ≤ 7 days at ED presentation and randomization.
- Signed informed consent

Criteria	Metric	Rationale
One or more symptoms of COVID-19 illness	Cough, shortness of breath or difficulty breathing, fevers, chills, repeated shaking with chills, muscle pain, headache, sore throat, new loss of taste or smell	CDC has defined a list of symptoms that include cough, shortness of breath or difficulty breathing, fevers, chills, repeated shaking with chills, muscle pain, headache, sore throat, or new loss of taste or smell. For purposes of this trial symptoms include any symptoms of COVID-19 illness listed by the CDC case definition guidance at the time of enrollment. Symptomatic COVID-19 illness justifies therapy. Asymptomatic illness is unlikely to be present in the emergency department unless it is an incidental finding.
Laboratory-confirmed SARS-CoV-2 infection	Local laboratory approved test for acute infection with SARS-CoV-2	Target illness is present. Testing for the presence of virus continues to improve at different sites over time. Tests should be specific and results available prior to enrollment. This should be their first episode of COVID-19 illness. See MOP for additional details.

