### **6.3 Measures to Minimize Bias: Randomization and Blinding**

A web-based central randomization system will be developed by the SIREN DCC and installed on the WebDCU™ study website. Allocation will be fixed using a 1:1 allocation ratio. The objective of randomization is to prevent possible selection bias by providing random treatment assignment to each subject and to prevent accidental treatment imbalances for known prognostic variables. Variables that will be included in the randomization scheme are: age (treated as a continuous variable) and site. Site is included in the randomization scheme to avoid severe treatment imbalances within each site. Randomization will occur via the study-specific password-protected website accessed by an authorized research coordinator or investigator at the clinical site. If, in rare circumstances, the web system is not available, the coordinator or investigator will have access to emergency randomization procedures that will allow the site to randomize the subject. Subjects will be considered randomized in this trial at the time of randomization, regardless of whether or not they receive the assigned study treatment.

The primary outcome assessment in this trial will be performed by study team members who are blinded to study group allotment. To test the effectiveness of blinding procedures, subjects will be asked at the Day 2 and Day 15 follow-up assessment to which treatment arm they believe they were assigned and how confident they are in their response. If the subject becomes knowledgeable of their treatment assignment at any point during study participation, this will be documented in the study database. Regardless of unblinding, the subject will remain in the study and be part of the analysis population.

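### Age and site are balanced at randomization but left out of the final primary comparison: a valid test, mildly conservative if they are prognostic, with a small power gain available

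*Combined protocol and SAP*

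**What the plan says.** Section 6.3 states that one aim of the allocation scheme is to "prevent accidental treatment imbalances for known prognostic variables", and continues: "Variables that will be included in the randomization scheme are: age (treated as a continuous variable) and site". The Randomization paragraph of section 1.2 agrees: the algorithm is to "prevent accidental treatment imbalances in age and site".

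Section 9.2.1 defines the primary test as the posterior probability that the event proportion is higher on saline than on CP. Success requires at least 0.975, chosen to match a one-sided 0.025. For the prior, "we assume a non-informative beta distribution for the prior probability"; no covariate is named. The same section then says: "Secondary analyses of the primary outcome will explore the impact of potential prognostic variables including age, sex, onset of symptoms duration and site". Those analyses use logistic regression. Nothing in the documents carries age or site into the primary comparison or explains why they are left out.

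On planning values, section 9 says "We believe that clinicians will change practice if CP can afford ~10% absolute risk reduction in disease progression", and section 9.1 says "we do not expect the proportion in the standard of care arm to vary greatly from 20" per cent. Section 9.1 gives 85% power for a 10-point decrease from 20% with 300 per arm. Sections 1.1 and 1.2 give the current maximum as 900 (450 per arm).

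**The concern.** Balancing allocation on prognostic factors removes part of the chance variation between arms. An analysis that ignores those factors still counts that variation, so its posterior is wider than the design warrants. The decision rule is then stricter than the 0.025 it was meant to match, and a little power is forgone. If neither factor predicts the endpoint, nothing is lost.

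The plan calls the balancing variables prognostic, holds both for every patient at randomization, and already intends a logistic model with them. An improvement is therefore available from data in hand. It concerns the efficiency of the final primary analysis, not its validity.

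**Working it through.** **Inputs from the documents.** One-sided 0.025 (section 9.2.1); 20% control rate, 10-point decrease, 300 per arm, 85% power (section 9.1); 450 per arm (sections 1.1, 1.2); looks at 33%, 50% and 75% with an efficacy threshold of 0.999 (section 9.2.2); at least 30 sites (section 5.4). Section 9.1 also discusses control rates near 30% and differences of roughly 8 points.

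**Assumptions.** R², the share of outcome variance explained by age and site, is set at 2%, 5% and 10%; the documents give none. The prior is taken as Beta(1,1), since its parameters are not stated.

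**Step 1: the plan's own figure.** The usual fixed-sample formula for 20% vs 10%, 300 per arm, gives (0.10 − 1.96 × 0.02915)/0.02887 = 1.485, or 93.1% power. The stated 85% is not reproduced. Continuity correction gives 91.5%, 10% missing data 90.4%, and the current looks with futility always followed 87.4%. None of this involves covariates, so it is a separate matter.

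**Step 2: upper bound on the gain.** Let V = [pc(1−pc) + pt(1−pt)]/n, z = (pc−pt)/√V and s = √(1−R²). With full balance and no looks:

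- unadjusted error = 1 − Φ(1.96/s)
- unadjusted power = Φ(z/s − 1.96/s)
- adjusted power = Φ(z/s − 1.96)

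The two power expressions share z/s and differ only in the critical value. Under full balance, the whole gain therefore comes from bringing the error back up to 0.025.

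Unadjusted error is 0.0239, 0.0222 and 0.0194 at R² 2%, 5% and 10%.

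Example: 30% vs 22%, 450 per arm, R² 10%. V = (0.21 + 0.1716)/450 = 0.000848; z = 0.08/0.02912 = 2.747; s = 0.9487. Unadjusted power is Φ(0.787/0.9487) = 79.7%; adjusted power is Φ(2.896 − 1.96) = 82.5%; gain 2.9 points.

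| Scenario | Power at R² 0 | Bound at R² 2% | 5% | 10% |
|---|---|---|---|---|
| 20% vs 10%, 450/arm | 98.9% | +0.1 | +0.1 | +0.2 |
| 30% vs 20%, 450/arm | 93.7% | +0.2 | +0.6 | +1.1 |
| 30% vs 22%, 450/arm | 78.4% | +0.6 | +1.4 | +2.9 |
| 20% vs 10%, 300/arm | 93.4% | +0.2 | +0.6 | +1.1 |
| 30% vs 20%, 300/arm | 81.3% | +0.5 | +1.3 | +2.6 |
| 20% vs 12%, 300/arm | 76.7% | +0.6 | +1.5 | +3.0 |

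**Step 3: the model proposed under the fix, simulated.** 20,000 trials per power scenario and 40,000 per null; 30 sites (600 patients) or an assumed 40 (900), unequal in size; an assumed biased coin of 0.8 on site, age and overall imbalance, because the documents do not give the algorithm.

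| Scenario | R² 0 | 2–3% | 4–5% | 9–11% |
|---|---|---|---|---|
| Gain, 20% vs 10%, 300/arm | 0.0 | +0.1 | +0.1 | +0.5 |
| Gain, 20% vs 10%, 450/arm | 0.0 | 0.0 | 0.0 | +0.2 |
| Gain, 20% vs 12%, 300/arm | −0.1 | 0.0 | +0.4 | +1.8 |
| Gain, 30% vs 22%, 450/arm | 0.0 | +0.4 | +0.8 | +2.4 |
| Error, unadjusted (20%, 300/arm) | 0.0252 | 0.0234 | 0.0231 | 0.0202 |
| Error, model (20%, 300/arm) | 0.0252 | 0.0236 | 0.0241 | 0.0230 |

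The paired standard error of a gain is 0.01 to 0.12 points, and that of an error rate about 0.0008. A smaller and noisier simulation (3,000 trials per scenario, minimization, logistic model with age and site) gave +0.1 to +1.5 points at 20% vs 10%, 300 per arm, for R² of 1.6% to 9.8%.

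**Step 4: overall error with the looks.** Brownian paths, efficacy stop at z > 3.09 (0.999), final test at 1.96, futility ignored. The comparison must be made at the same R²:

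| Final test | R² 2% | 5% | 10% |
|---|---|---|---|
| Unadjusted (current plan) | 2.47% | 2.29% | 2.00% |
| Adjusted final, unadjusted looks | 2.58% | 2.57% | 2.55% |

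At R² 0 the current plan gives about 2.58%. A repeat run agreed within about 0.02 points. If futility were always followed, the current plan's error at R² 0 would be about 2.0%.

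**The case against.** The case for leaving the plan alone is strong. The test is valid. The planned logistic analyses will show age and site anyway. R² has no source in the documents, and two features may keep it small: section 8.1.1 counts admission for any reason, and section 5.1 requires that every patient "Has at least one study defined risk factor for severe COVID-19 illness", which narrows the range of risk. Section 6.3 includes site only to avoid severe imbalance, so the full balance behind the bound is not promised. The gain is largely error rate that the unadjusted test leaves unspent. The change would also come after an interim look has apparently taken place. All of this stands. It limits the point to optional efficiency but does not remove it, because the plan itself balances on these factors and holds the data.

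Three stronger readings are tempting and not supported:

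- **That the primary test is invalid or inflates false positives.** The effect runs the other way: ignoring balanced prognostic factors lowers the error.
- **That the omission undermines the stated 85% power, or costs about a point at the plan's target.** Unadjusted power at 20% vs 10% exceeds 93% in a fixed sample. The 1.1-point figure is an upper bound at 300 per arm and R² 10%; at the current 450 per arm it is 0.2.
- **That adjusting leaves the overall error unchanged.** That holds only against the current plan at R² 0. At the same R², it rises by about 0.1 to 0.55 points.

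**Conclusion.** Minor. The final primary comparison omits the two factors used in allocation. It remains valid and is mildly conservative if those factors are prognostic and well balanced.

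At 450 per arm the ideal gain from adjustment is 0.2 points or less at 20% vs 10%, 0.2 to 1.1 at 30% vs 20%, and 0.6 to 2.9 at 30% vs 22%. The simulated gain of a workable model is smaller: 0 to 0.5 points at 20% vs 10% over both sample sizes. The loss is largest where power is not already high. A control rate near 30% is a possibility, not a documented fact: section 9.1 links a larger sample to an event rate above the assumed one, but does not say what drove the increase to 900.

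These sizes rest on assumed R² values of 2% to 10%, near-complete balance for the bound, and an assumed allocation algorithm for the simulation. The conclusion covers the final primary analysis only.

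**What to change.** Make the final primary analysis a prespecified Bayesian logistic model with treatment, continuous age and a partially pooled site intercept. State the priors; for example, Normal(0, 2.5) on the treatment and standardized-age coefficients, Normal(0, 5) on the intercept and half-normal(0.5) on the site SD. Keep the 0.975 threshold. Report the standardized risk difference with its credible interval, so that the result stays on the absolute-risk scale. Keep the beta-binomial comparison as a sensitivity analysis.

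No new data are needed. The costs to state are:

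1. **Error rate.** With the 0.999 looks and futility ignored, overall one-sided error moves from slightly below 2.5% to slightly above it, close to the current plan's level at R² 0. Check this by simulation under the actual allocation algorithm.
2. **Futility.** The predictive probability in section 9.2.2 should be computed for the adjusted final test, or the mismatch stated. The efficacy looks may stay unadjusted, since sites are sparse early.
3. **Missing data.** The sensitivity rule in section 9.2.3 must be applied to the adjusted model, where the answer depends on which patients are missing and not only on arm counts.
4. **Sparse sites.** There are about 20 to 23 patients per site on average (600/30 = 20; 900 over an assumed 40 sites = 22.5), so the model relies on pooling.
5. **Timing.** Re-estimation is tied to the first interim and the maximum is already 900, so that look has apparently occurred. The change must be fixed and dated by staff blinded to arm-level results and reported to the DSMB.

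If the sponsor judges that this gain does not justify a mid-trial change, the current analysis can stand, with the reason for omitting the balancing factors recorded.
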